Dyspepsia refers to chronic or recurrent upper gastrointestinal symptoms. According to the Rome IV criteria, functional dyspepsia (FD) symptoms included meal-related fullness, early satiation, epigastric pain or burning which are unexplained after routine investigation. FD causes substantial psychophysical burden because of its unknown etiology and high prevalence. Although FD is currently associated with local inflammation of the gastrointestinal tract and microbiota alteration, current available treatments for FD are of limited effectiveness. In view of this, many studies have applied Chinese herbal medicine in FD and achieved some therapeutic benefit. The Jing Si Herbal Tea Liquid Packet composed of eight native Taiwanese herbs (wormwood, hickory grass, *Ophiopogon japonicus*, *houltuynia cordata*, platycodon, licorice, perilla leaves, chrysanthemum) has obtained a special export license from the Ministry of Health and Welfare. The Jing Si Herbal Tea Liquid Packet also has been registered in clinical trials as a complementary treatment for COVID-19. The preliminary data demonstrated that the Jing Si Herbal Tea Liquid Packet may improve gastrointestinal symptoms and anxiety in patients with COVID-19. Therefore, this study aims to investigate the impact of the Jing Si Herbal Tea Liquid Packet on psychophysical burden and metabolites of microbiota in patients with FD through a double-blind randomized manner.

關鍵詞： functional dyspepsia; Jing Si Herbal Tea Liquid Packet; psychophysical burden

G. Background and purpose of the research project

Please describe in detail the background, purpose, importance of this research project and the research situation related to this project at home and abroad,
Comments on important references, etc., please write in Chinese format.

Background

Symptoms of the new crown-gut-brain axis disorder (disorders of gut-brain interaction, DGBI)

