
Changes in the bacterial phase of the new crown symptoms

SARS-CoV-2 infection caused significant changes in the intestinal flora of patients. The number of

potential pathogens in the patient's body increases, and the antibiotic treatment also reduces the beneficial bacteria.⁹ Hazan et al. (2022) showed reduced gut bacterial diversity in infected individuals, with reduced numbers of Bifidobacterium, Faecalibacterium, and Roseburium.¹⁰ At six months post-infection, the intestinal bacterial diversity of the patients was still significantly low.¹¹ In addition to reduced diversity, these symptomatic patients had lower numbers of anti-inflammatory bacteria such as Faecalibacterium prausnitzii, Eubacterium rectale, Bifidobacterium adolescentis, and potential pathogens such as Rothia, Erysipelatoclostridium, Ruminococcus gnavus in the gut three months after infection. , Ruminococcus torques, and Bacteroides dorei are more.¹² Su et al. (2022) studied the dysbiosis caused by post-acute COVID-19 syndrome and found that there were more potential pathogens such as Erysipelatoclostridium ramosum and Ruminococcus gnavus, and beneficial bacteria Bifidobacterium adolescentis, B. pseudocatenulatum) decreased.¹³ These evidences show that the intestinal flora has not fully recovered from the imbalance during infection, and is still in a state of low diversity and favorable pathogens, which can continue to cause immune responses in the intestine. Functional dyspepsia is also thought to be caused by increased permeability of the intestinal wall of the small intestine, allowing intestinal microbial metabolites to infiltrate the tissues and activate the immune system.¹⁴

In both functional dyspepsia and irritable bowel disorder, there is marked dysbiosis in the gut. Bacterial changes in patients with functional dyspepsia include decreased numbers of Bacteroidetes (Prevotellaceae) and increased numbers of Proteobacteria, Firmicutes (Streptococcus and Clostridia) and Bifidobacteria.¹⁵ Bacterial changes in IBD included increased Clostridia (increased Ruminococcus but decreased Faecalibacterium), increased Lactobacillus and Streptococcus within the phylum Firmicutes, increased Bacteroides, and decreased Bifidobacteria.¹⁶ After synthesis, it can be seen that the changes in the gut-brain axis disorder are mainly due to the replacement of Bacteroidetes by Firmicutes, while the changes in the number of Proteobacteria and Bifidobacteria are inconsistent.

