Jing Si Herbal Tea Liquid Packet

The ingredients of Jing Si Herbal Tea Liquid Packet are mugwort leaves, houttuynia cordata, Ophiopogon japonicus, Houttuynia cordata, Campanulaceae, licorice, perilla leaves, chrysanthemum and other eight native Taiwanese herbs that can clear away moisture, dispel cold, relieve lungs and resolve phlegm, and clear away dampness and heat. Chinese medicinal herb, current research has found that it can block the combination of the new coronavirus and cells, and can also reduce cell penetration and block the virus from penetrating cells, while targeting wild-type and mutant viruses D614G, B.1.1.7, 501Y.V2 Carrying out animal studies, it was found that Jing Si Herbal Tea Liquid Packet can reduce the ability of 60 to 70% of the virus to infect the upper respiratory tract, lung, heart, and intestine of mice and reduce the expression of FKBP51, a protein related to depression, by 40%. The effect of using Jing Si Herbal Tea Liquid Packet to help reduce the amount of virus and systemic anti-inflammatory effect in patients with COVID-19. (9) In our

Version date : (Version 3, 11/10/2022)

ongoing clinical study, for functional dyspepsia (FD) patients, Jing Si Herbal Tea Liquid Packet can improve symptoms in 75% of patients, compared with only 33% of placebo.

Purpose

A double-blind randomized trial was conducted to investigate the improvement of Jingsi Bencao decoction concentrate on the physical and mental symptoms of gut-brain axis disorder (DGBI) and the changes in intestinal flora after COVID-19.

Importance

Gut-brain axis disorders (DGBI), including functional dyspepsia and irritable bowel syndrome, are gastrointestinal problems after COVID-19 infection. They are also diseases that are worthy of improvement in the efficacy of traditional Western medicine. The discovery that Jingsi Bencao Drink Concentrate improves gastrointestinal function and depression after infection with the new coronavirus can be used to improve the physical and mental symptoms of gut-brain axis disorder (DGBI).

※If there are not enough fields, please copy by yourself.

H. Research methods, steps and implementation progress

1. Please describe in detail the research methods and reasons used in this project.
2. Estimated possible difficulties and solutions.
3. If it is a continuous plan, the research progress report or primary data of the previous year should be attached at the same time.
4. Please write in Chinese format.

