pneumonia will be recruited in the outpatient department of gastroenterology, including 75 subjects with functional dyspepsia (FD) and 75 subjects with irritable bowel syndrome (IBS) subjects; qualified subjects will receive blood and feces sampling and complete physical and mental symptom assessment (sleep habits questionnaire, anxiety questionnaire, stress questionnaire, gastrointestinal symptoms questionnaire, and irritable bowel syndrome questionnaire) before treatment, and then according to the double-blind random allocation method, the computer generated garbled characters, and assigned Jing Si Herbal Tea Liquid Packet or placebo according to the coding sequence, and the research assistant gave Jing Si Herbal Tea Liquid Packet or placebo, Host and recipients None of the subjects knew what the content of the assignment was. The experimenters took Jing Si Herbal Tea Liquid Packet or placebo in the first month, and after the end of the month, they received blood and stool tests and complete physical and mental symptom assessment (sleep habits questionnaire, anxiety questionnaire, stress questionnaire), gastrointestinal symptom questionnaire, and irritable bowel syndrome questionnaire), the laboratory will conduct pre- and post-test analysis of LC-MS and intestinal bacteria, and then conduct a cross-test. The original placebo will take Jing Si Herbal Tea Liquid Packet in the second month, previously taking Jing Si Herbal Tea Liquid Packet will take a placebo in the second month, after the end of the second month, do the third complete physical and mental symptom assessment (sleep habits questionnaire, anxiety questionnaire, stress questionnaire, digestive tract Symptom Questionnaire, Irritable Bowel Disorder Questionnaire), the test is completed.

Research flow chart

3. Questionnaire

The questionnaire items included sleep habits questionnaire, anxiety questionnaire, stress questionnaire, gastrointestinal symptoms questionnaire, and irritable bowel syndrome questionnaire. The details of the questionnaire are attached.

4. Collection, preservation, transportation and DNA extraction of feces

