Fix the collection box on the toilet lid, discharge fresh feces into the collection box, then screw the lid tightly and place it in a zipper bag within 4 hours or in a -4°C refrigerator within 24-48 hours Sent to the laboratory for sub-packaging, and then refrigerated in a -80°C refrigerator. Thaw when the DNA is extracted, the extraction process includes the following steps sample homogenization, cell lysis, non-DNA material removal and DNA purification.

5. Gut microbiota sequencing and community analysis

In this study, 16S rDNA massively parallel sequencing will be used to analyze the composition of gut bacteria. 0.25 g of stool samples were pooled for DNA extraction with the QIAmp PowerFecal Kit (Qiagen, Hilden, Germany). The purified DNA was PCR'd with primers for 341F and 805R to amplify the V3-V4 fragments of the 16S rRNA gene, and the barcode was sent to the manufacturer for library building. The Illumina MiSeq platform was used for next-generation pair-end sequencing. Sample 30000 reads. After the sequence obtained by the manufacturer was screened for high-quality fragments by Mothur and Usearch software, the bacterial phase composition and taxonomic status of each sample were calculated. The taxonomic status of each sequence was determined by comparing the Mothur software with the SILVA sequence database. The investigators will use Microbiome Analyst R and other suitable R programming language packages to perform cluster analysis and network analysis of bacterial composition.

6. Stool and Blood LC-MS Analysis

I. Plasma sample collection and preparation :

Whole blood was collected in Vacutainer K2E-EDTA (BD Diagnostics, Franklin Lakes, NJ, USA) blood collection tubes. The collected whole blood samples were then transferred to 15 mL containing Ficoll-paque PLUS medium [whole blood (all blood)/ Ficoll-paque PLUS medium = 4/3 (volume ratio v/v)] (GE Healthcare Life Sciences, Pittsburgh, PA, USA) and centrifuge (3000 rpm, 30 min) at room temperature. After centrifugation, the plasma (plasma) supernatant that was successfully layered was collected and distributed into sterilized 1.5 mL microcentrifuge tubes (Eppendorf), and glacial acetic acid with a concentration of 1 N and a volume of 1% was added.) aqueous solution to prevent the degradation of the analyte in plasma. Plasma is stored in a freezer at -80°C, and the storage period does not exceed 1 year.

II. Previous processing method of Lipophilic Substances :

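### The randomised trial has a flora and metabolite aim, but the protocol names only pre/post and cluster/network analyses for these data and limits its tea-versus-placebo test to questionnaires

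*Protocol*

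**What the plan says.** **Aim.** The Purpose in Section G describes a double-blind randomised trial whose subject matter includes "the changes in intestinal flora after COVID-19". The English summary (Section F) says that the trial studies the product's impact on "psychophysical burden and metabolites of microbiota in patients with FD through a double-blind randomized manner".

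**Design and sampling.** In Section H.2 subjects give blood and stool before treatment and are then "assigned Jing Si Herbal Tea Liquid Packet or placebo according to the coding sequence". Of those taking either product in month 1, the section says that "after the end of the month, they received blood and stool tests". After the exchange of products, the visit at the end of month 2 lists questionnaires only.

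**Analyses named for the laboratory data.** Section H.2 states that "the laboratory will conduct pre- and post-test analysis of LC-MS and intestinal bacteria, and then conduct a cross-test". Section H.5 says that the investigators will "perform cluster analysis and network analysis of bacterial composition". Neither section names a contrast between tea and placebo.

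**Treatment comparison.** Section H.8 defines the treatment effect as percentage improvement on a list of named questionnaires and compares tea with placebo by a chi-squared test on that improvement. No flora or LC-MS variable is in the list.

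**Background.** Section G concludes from earlier studies that "the intestinal flora has not fully recovered from the imbalance during infection". It gives no rate of recovery.

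**The concern.** A randomised aim needs a randomised contrast. A within-subject change over one month combines any product effect with whatever else moves over that month: continuing recovery after infection, diet, ordinary fluctuation, or differences between laboratory runs if before and after samples are processed apart. Cluster and network analyses describe structure in the data and do not estimate the difference that the product makes.

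The trial will hold concurrent placebo samples that can separate these explanations, but the protocol does not say that they will be used for this purpose. At stake is a claim that the tea altered flora or metabolites when the placebo group altered equally. Table 2 lists 22 analytes apart from internal standards, and the taxa come on top, so the opportunity for such a claim recurs many times.

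**Working it through.** **1. Aims against analyses**

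| Outcome | Among the trial's aims | Analysis named | Tea versus placebo named |
|---|---|---|---|
| Questionnaires | Yes (G, F) | Percentage improvement, chi-squared (H.8) | Yes |
| Flora | Yes (G) | Pre/post (H.2); cluster and network (H.5) | No |
| Metabolites (LC-MS) | Yes (F) | Pre/post (H.2) | No |

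**2. Where randomised laboratory data exist**

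Blood and stool are listed before treatment and after month 1, and not after month 2. The crossover therefore adds nothing to this aim. The only randomised contrast is the parallel comparison of arms at month 1.

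**3. Size of the risk (illustration)**

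The plan has no figure of its own to reproduce here. The sample size in Section H.9 is based on symptom response in functional dyspepsia.

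Inputs:
- From the documents: 150 subjects planned and at least 100 required (H.9); significance level 0.05 (H.8).
- Assumed: 1:1 allocation, so 75 or 50 per arm; two-sided testing; no tea effect; equal drift of d standard deviations of the change score in both arms.

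The paired test within the tea arm has noncentrality d × √n on n − 1 degrees of freedom. For d = 0.2 and n = 75 this is 0.2 × 8.66 = 1.73, against a critical value of 1.99.

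| Drift d | Tea arm alone, n = 75 | Tea arm alone, n = 50 | Between arms |
|---|---|---|---|
| 0.1 | 13.7% | 10.7% | 5% |
| 0.2 | 40.1% | 28.4% | 5% |
| 0.3 | 72.7% | 54.8% | 5% |
| 0.4 | 92.8% | 79.2% | 5% |

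The entries are the chance of a significant result when the tea does nothing. The between-arm test stays at 5% because equal drift cancels.

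**4. What the randomised comparison can detect**

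For 80% power the detectable difference in mean change is (1.96 + 0.84) × √(2/n) SD:
- n = 75 per arm: 2.80 × 0.163 = 0.46 SD
- n = 50 per arm: 2.80 × 0.200 = 0.56 SD

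These figures are before any gain from baseline adjustment and apply to one outcome, without allowance for multiple testing.

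**The case against.** The strongest reply is that this is silence, not a wrong plan. The sentence in Section H.2 sits in a description of procedures and can be read as assaying the before and after samples. Section H.5 is a sequencing pipeline that leaves room for other R packages. Section H.8 also uses before-and-after language for the questionnaires and then compares the arms, so in this protocol the change may simply be the measure, with randomisation supplying the contrast. A statistical analysis plan, not shown here, may say so.

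Much of this stands. A reader might infer that natural recovery will be credited to the tea, or that the placebo arm goes unused in the laboratory work. The documents support neither. Month-1 samples come from takers of either product, the budget line for LC-MS and intestinal bacteria has a quantity of 150, which matches the full planned sample, and nowhere is the pre/post analysis confined to the tea arm.

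The mechanism is also less certain than it may seem. Section G stresses persistence, with diversity still low at six months, and says nothing about change within one month. That passage concerns flora, not plasma metabolites. Regression to the mean is indirect at best, because no entry criterion selects on flora or on the LC-MS analytes. The order of laboratory processing is not stated, so drift between runs is only a possibility.

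The reply does not dispose of the point. The protocol is not silent about these data: it names analyses for them, and none of those named answers the randomised aim. It also writes an arm comparison and lists the outcomes to which it applies, leaving these out.

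**Conclusion.** The point holds in a limited form. The protocol states a randomised flora and metabolite aim, names only pre/post and cluster/network analyses for it, and restricts its tea-versus-placebo test to questionnaires. Followed as written, a change over month 1 could be attributed to the tea when placebo subjects changed equally.

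The percentages above show the direction of the risk and how quickly it grows. They are not an error rate of this plan: they rest on a tea-arm-only paired test that the protocol does not specify, on assumed drift, and on every assigned subject being evaluable. The conclusion itself rests on setting Sections F, G, H.2, H.5 and H.8 side by side and needs none of those assumptions. The design and sampling are adequate for a valid month-1 comparison. The gap is in the stated analysis, and it should be closed before the laboratory data are analysed.

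**What to change.** In Section H.8, state that the flora and metabolite aim is answered by the randomised tea-versus-placebo comparison at month 1, adjusted for each subject's own baseline value and for diagnosis (functional dyspepsia or irritable bowel syndrome). In Sections H.2 and H.5, label within-arm pre/post, cluster and network results as descriptive. Note that month 2 does not contribute to this aim because no blood or stool sampling is listed then.

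The choice of taxa, transformations and the test for overall composition can be left to the statistical analysis plan.

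The cost is wording and slightly more analysis, with no new samples. The sponsor should accept that a flora claim becomes harder to reach than with a pre/post test.

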Thaw the plasma sample at room temperature for 10-20 minutes, then transfer 100 μ L of plasma to a new 1.5 mL microcentrifuge tube. Add the internal standard (internal control, 13C-PA) first, then add methanol 3 times the volume of plasma for deproteinization, and let it stand at room temperature for about 15-20 minutes. Then centrifuge the rested microcentrifuge tube (3,000 rpm, 10 min, 4 $^{\circ}$ C), and transfer the supernatant to the corresponding small glass test tube. Move the glass test tubes to a nitrogen blowing system, dry the samples through a nitrogen flow, and then add 100 μ L of chloroform (Chloroform) to each sample for redissolution. A filtration extraction system was set up, and solid phase extraction columns [Solid phase extraction (SPE) columns (Strata-X-C 33 μ m polymeric strong cation 60 mg/3 mL, Phenomenex, Torrance, CA, USA)] were used for extraction. Add 1.0-1.5 mL of n-hexane (hexane) solution to the erected column to activate the column, and use a vacuum pump to pump positive pressure for about 20-30 seconds. Replace the glass test tubes that have been filled with n-hexane solution under the filter extraction system, and then add the samples to the activated column in sequence. Add 1.0-1.5 mL of ethyl acetate (ethyl acetate) for vacuum extraction for about 30-45 seconds, and transfer the sample extracted with ethyl acetate to a nitrogen blowing system to dry it. Redissolve the sample with 100 μ L of methanol, and finally transfer the reconstituted sample to a liquid chromatography-mass spectrometer (LC-MS) vial equipped with insert, and prepare for analysis on the machine with an injection volume of 30 μ L per needle .

III. Hydrophilic Substances before the processing method :

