48.0	1	99	6
48.4	85	15	6
60.0	85	15	6
Condition II (Hydrophilic Substances)			
Mobile phase A		Mobile phase B	
0.1% Formic acid in 99.9% ddH ₂ O		0.1% Formic acid in 99.9% MeOH	
Time (min)	%A	%B	Curve
0	95	5	6
14	30	70	6
16	30	70	6
18	50	50	6
MS conditions			
Detector	Waters ACQUITY QDa (Performance)		
Ionization mode	ESI Negative (I); ESI Negative and Positive (II)		
Capillary voltage	Default (0.8 kV)		
Probe temp	Default (600°C)		
Cone voltage	20V(I); 15V(II)		
Sampling rate	8 Hz		
Full scan	250-600 m/z for Negative (I); 70-600 m/z for Negative or Positive		
SIR	See Table 2 - "Molecular Ions (m/z)"		

e. Method validation :

Including Limits of detection, LOD and Limits of quantitation, LOQ, Calibration curve, Recovery, accuracy and precision, Intra-assay, accuracy and precision and Inter-assay precision and accuracy of each test substance.

Table 2. LC-MS analysis Standard List:

	Molecular ion (m/z)	Ion source mode

Lipophilic Substances			
Short Chain Fatty acids (SCFAs)	Acetate (2:0)	42.0+153 (3NPH)	ESI Negative
	Propionate (3:0)	57+153 (3NPH)	ESI Negative
	Butyrate (4:0)	72+153 (3NPH)	ESI Negative
Long Chain Fatty acids	Palmitic acid, PA (16:0)	255.1	ESI Negative
	Stearic Acid, SA (18:0)	283.2	ESI Negative
	Palmitoleic Acid, POA (16:1)	253.2	ESI Negative
	Oleic Acid, OA (18:1)	281.2	ESI Negative
Fatty acid esters of hydroxy fatty acids (FAHFAs)	Palmitoleic Acid Ester of 9-Hydroxystearic Acid (9-POHSA)	535.5	ESI Negative
	Oleic Acid Ester of 9-Hydroxystearic Acid (9-OAHSA)	563.5	ESI Negative
Internal standards			
	[¹³ C ₁₆]- Palmitic acid (IS1)	271.4	ESI Negative
Hydrophilic Substances			
Methionine cycle	L -Methionine (L -Met)	150.1	ESI Positive
	S -adenosyl- L -methionine (SAM)	399.0	ESI Positive
	S -adenosyl- L -homocysteine (SAH)	385.0	ESI Positive
	L -Homocysteine (L -Hcy)	136.1	ESI Positive
	Methylmalonic acid (MMA)	117.1	ESI Negative
Antioxidants	Ascorbic acid (AA)	174.9	ESI Negative
Nutrition index	3-Methyl- L -histidine (3-MH)	170.0	ESI Negative
Fatty acids carrier	L -Carnitine (L -Car)	162.1	ESI Positive
	Acetyl- L -Carnitine (ALC)	204.0	ESI Positive
	Propionyl- L -Carnitine (PLC)	218.0	ESI Positive
Nephrotoxin	Trimethylamine N -oxide (TMAO)	76.0	ESI Positive
	Indoxyl Sulfate (InS)	211.9	ESI Negative
	p -Cresyl sulfate (pCS)	187.0	ESI Negative
Internal standards			

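### Table 2 gives three short-chain fatty acid masses that cannot all be right, and no derivatisation step is written; if acetate is read in plasma, the acetic acid stabiliser would also dominate its signal

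*Protocol*

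**What the plan says.** All places are in the Protocol, section H, item 6, unless noted.

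- **Table 2** lists acetate, propionate and butyrate among the lipophilic substances. Their molecular ions are 42.0+153, 57+153 and 72+153, each labelled 3NPH and ESI Negative. The selected ion recording (SIR) row of **Table 1** points to this column for the channels to monitor.
- **Table 1** sets the full scan for condition I, the lipophilic run, at "250-600 m/z for Negative (I").
- **Part II** (lipophilic preparation) starts from thawed stored plasma: "Add the internal standard (internal control, 13C-PA) first, then add methanol 3 times the volume of plasma for deproteinization". Drying, chloroform, solid-phase extraction, drying again and methanol follow, and the sample then goes to the vial. **Part III** (hydrophilic preparation) also starts from plasma. Neither part mentions 3NPH.
- **Part I** says of the collected plasma that "glacial acetic acid with a concentration of 1 N and a volume of 1% was added", as an aqueous solution, "to prevent the degradation of the analyte in plasma". No acid-free aliquot is described.
- The item is headed "Stool and Blood LC-MS Analysis", but no stool preparation for LC-MS is given and no matrix is named for the short-chain acids.
- **Part e** plans method validation for each test substance: detection and quantitation limits, calibration curve, recovery, accuracy and precision.
- Section H, item 2 says that "the laboratory will conduct pre- and post-test analysis of LC-MS and intestinal bacteria". The English summary (section F) gives as its aim the effect on "psychophysical burden and metabolites of microbiota in patients with FD".

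**The concern.** The background in section G names six bacterial metabolites: acetate, propionate, butyrate, TMAO, indoxyl sulfate and p-cresyl sulfate. The Table 2 problem touches three of these six, and three of the 22 analytes listed. A laboratory that followed the text would monitor the wrong channels for acids that the text never tells it to derivatise. The condition I scan starts at 250, above all three ions, so it would not show the mistake.

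The stabiliser raises a separate question. Acetic acid is itself one of the analytes. Added acetate cannot be told apart from the subject's own, and the lipophilic internal standard is labelled palmitic acid, not labelled acetate. If plasma acetate is measured in these tubes, most of what is measured was put there by the laboratory.

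**Working it through.** **1. Internal check of the masses (Table 2 only).**

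The listed sums are 42.0+153 = 195, 57+153 = 210 and 72+153 = 225. Acetate, propionate and butyrate have 2, 3 and 4 carbons, so each step adds one CH2.

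| Pair in Table 2 | Listed | Step | CH2 units | Per CH2 |
|---|---|---|---|---|
| acetyl- to propionyl-carnitine | 204.0 to 218.0 | 14.0 | 1 | 14.0 |
| palmitic to stearic acid | 255.1 to 283.2 | 28.1 | 2 | 14.05 |
| palmitoleic to oleic acid | 253.2 to 281.2 | 28.0 | 2 | 14.0 |
| 9-POHSA to 9-OAHSA | 535.5 to 563.5 | 28.0 | 2 | 14.0 |
| acetate to propionate | 195 to 210 | 15 | 1 | 15 |
| propionate to butyrate | 210 to 225 | 15 | 1 | 15 |

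All three acids carry the same label and ion mode. Any two of them differ by 15 or 30 where the table's own spacing requires 14 or 28, so at most one of the three can be right. This needs nothing from outside the document.

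**2. What the ions would be.** Assumption: 3NPH is 3-nitrophenylhydrazine (153.054) and couples with loss of water (18.011). The document does not state this. The negative ion then loses one proton (1.007):

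ion = acid + 153.054 − 18.011 − 1.007

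| Acid | Acid mass | Neutral derivative | Negative ion | Positive ion | Listed | Listed − negative ion |
|---|---|---|---|---|---|---|
| acetate | 60.021 | 195.06 | 194.06 | 196.07 | 195 | 0.94 |
| propionate | 74.037 | 209.08 | 208.07 | 210.09 | 210 | 1.93 |
| butyrate | 88.052 | 223.10 | 222.09 | 224.10 | 225 | 2.91 |

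No single reading fits all three. As neutral derivatives only acetate fits. As positive ions only propionate fits, and the table says negative. Underivatised negative ions would be 59.01, 73.03 and 87.05, and none fits.

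**3. Control on the method.** The same mass calculation was run on 18 of the 19 other analytes in Table 2, and 17 agree within 0.15 (palmitic acid 255.23 against 255.1, oleic acid 281.25 against 281.2, p-cresyl sulfate 187.01 against 187.0). The exception is 3-methylhistidine, listed at 170.0 in negative mode. Its negative ion is 168.08 and its positive ion 170.09. Among the 11 negative-mode rows checked, 10 follow mass minus one proton.

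**4. Stabiliser (conditional on plasma acetate being read).** Acetic acid has one acidic proton, so 1 N is 1000 mmol/L. Adding 1% by volume gives

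1000 × 0.01 / 1.01 = 9.90 mmol/L.

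With native acetate x mmol/L in the tube (assumed; the documents give no value), the additive's share is 9.90 / (9.90 + x). A true doubling of native acetate would appear as a rise of x / (9.90 + x).

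| x (assumed) | Share from additive | Apparent rise on a doubling |
|---|---|---|
| 0.01 | 99.9% | 0.1% |
| 0.1 | 99.0% | 1.0% |
| 1 | 90.8% | 9.2% |

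The additive is the larger part for any x below 9.9 mmol/L. If drying removes acetate, it removes added and native acetate alike, so the share does not change. A dispensing error of 1%, 2% or 5% (assumed) is 0.10, 0.20 or 0.50 mmol/L of pure noise.

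**The case against.** **The stabiliser point may not arise.** Stool is collected, the item covers stool and blood, and the short-chain acids have no stated matrix. The lipophilic preparation as written has no 3NPH step, so it cannot be the complete method for acids listed as 3NPH derivatives. That weakens any inference that they are read in acidified plasma. This stands, and it is why the stabiliser point is secondary and conditional. A reader might infer that the acetate results are already lost; the documents do not establish that. What remains is that the only written preparation for this class of analytes starts from the acidified plasma.

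**A reader might infer that the additive biases the treatment comparison.** It does not in any direction that the documents imply. The addition is common to both arms and to both sampling times, so a constant amount cancels in an absolute difference. The harm is noise and a flattened percentage change.

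**Validation may catch the mass error.** Running derivatised standards, as part e would require, could expose channels that are 2 or 3 units off, and recovery work could reveal the acetate background. This lowers the practical risk but does not correct the text.

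**The replacement masses need outside chemistry.** This is true: 194, 208 and 222 hold only if 3NPH couples as assumed. The conflict of 15 against 14 per carbon does not depend on it. It would also be wrong to say that every other negative-mode entry is mass minus one proton, because 3-methylhistidine is not.

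**Relevance is low.** The Purpose in section G names symptoms and intestinal flora, and item 8 tests questionnaires only. This stands and sets the severity.

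**Conclusion.** The Table 2 error is firm: at most one of the three listed masses can be right, and no derivatisation step is written in either preparation. On the assumed coupling chemistry, the channels are about 1, 2 and 3 units too high for acetate, propionate and butyrate.

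The stabiliser point holds only if acetate is read from the acidified plasma. In that case the added 9.9 mmol/L is the larger part of the signal for any native level below 9.9 mmol/L, and about 91% to 99.9% at an assumed 1 to 0.01 mmol/L. It affects one analyte in one matrix. Stool acetate, propionate and butyrate are not touched by it.

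Severity is minor. These are laboratory read-outs that serve a stated aim but carry no planned test. The questionnaire comparisons, the 16S sequencing and the sample size do not depend on them.

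**What to change.** 1. Correct the three SIR masses in Table 2 to match the derivatisation actually used (194, 208 and 222 if the 3NPH products are the hydrazides assumed above), and add that step to the written preparation.
2. Check the 3-methylhistidine row: either the ion mode or the mass needs changing.
3. State the matrix for the short-chain acids and, if it is stool, give the stool preparation.
4. If it is plasma, stabilise with an acid that is not an analyte, or keep an un-acidified aliquot for these acids. Do not report plasma acetate from tubes that have already received acetic acid.

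Items 1 to 3 are text corrections. Item 4 is a small laboratory change: stability must be checked with the replacement acid or in the un-acidified aliquot, and a separate aliquot uses slightly more plasma. It is best done before samples are processed, because native acetate cannot be recovered from plasma that is already acidified.
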